Patients who test positive for a past or active Hepatitis B infection should be given prophylactic administration. If the patient has a positive Hepatitis B test result, they should be treated with Hepatitis B anti-viral lamivudine 100 mg prior to start of RAD001 therapy and throughout the treatment period with RAD001. Some associated toxicities to the lamivudine may include headache, diarrhea, and rash. If the patient needs to be treated with lamivudine, the cost of the treatment will be charged to the patient's insurance. For guidance on management of Hepatitis B and C reactivation, refer to Section 3.2.6.4.

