3.2.6.4 Management of Hepatitis B or C Reactivation

Monitoring and prophylactic treatment for hepatitis B reactivation

Table 3-2 provides details of monitoring and prophylactic therapy according to the baseline results of viral load and serologic markers testing.

Table 3-2 Action to be taken for positive baseline hepatitis B results

Test	Result	Result	Result	Result	Result
HBV-DNA	+	+ or -	-	-	-
HBsAg	+ or -	+	-	-	-
HBs Ab	+ or -	+ or -	+	+ or -	- or + with prior HBV vaccination
HBc Ab	+ or -	+ or -	+ or -	+	-
Recommendation	Prophylaxis treatment should be started 1-2 weeks prior to first dose of study drug Monitor HBV-DNA approximately every 6 weeks		No prophylaxis Monitor HBV-DNA approximately every 3 weeks		No specific action

Antiviral prophylaxis therapy should continue for at least 4 weeks after last dose of study drug. For patients who have already received study drug prior to the approval of the amendment, the same process should be followed at the patient's next visit. The first HBV-DNA result would be regarded as baseline. For hepatitis B reactivation, definition and management guidelines, see Table 3-3 Guidelines for management of hepatitis B.

Table 3-3 Guidelines for management of hepatitis B

HBV reactivation (with or without clinical signs and symptoms)*	
For patients with baseline results: Positive HBV-DNA OR positive HBsAg ----- reactivation is defined as: [Increase of 1 log in HBV-DNA relative to baseline HBV-DNA value OR new appearance of measurable HBV-DNA]	Treat: Start a second antiviral AND Interrupt study drug administration until resolution: ≤ baseline HBV-DNA levels If resolution occurs within ≤ 28 days, study drug should be re-started at one dose lower, if available. If the patient is already receiving the lowest dose of study drug according to the protocol, the patient should restart at the same dose after resolution. Both antiviral therapies should continue at least 4 weeks after last dose of study drug. If resolution occurs > 28 days, patients should discontinue study drug but continue both antiviral therapies at least 4 weeks after last dose of study drug.

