For patients with baseline results: Negative HBV-DNA and HBsAg AND [Positive HBs Ab (with no prior history of vaccination)	Treat : Start first antiviral medication AND Interrupt study drug administration until resolution: ≤ baseline HBV-DNA levels If resolution occurs within ≤ 28 days study drug should be re-started at one dose lower, if available. If the patient is already receiving the lowest dose of

against HBV), OR positive HBc Ab]	study drug according to the protocol, the patient should restart at the same dose after resolution. Antiviral therapy should continue at least 4 weeks after last dose of study drug.
reactivation is defined as:	If resolution occurs > 28 days, patients should discontinue study drug but continue antiviral therapy at least 4 weeks after last dose of study drug.
New appearance of measurable HBV-DNA	

* All reactivations of hepatitis B are to be recorded as grade 3 (CTCAE v 3.0 Metabolic Laboratory/Other: Viral Re-activation), unless considered life threatening by the investigator; in which case they should be recorded as grade 4 (CTCAE v 3.0 Metabolic Laboratory/Other: Viral Re-activation). Date of viral reactivation is the date on which **both** DNA and ALT criteria were met (e.g. for a patient who was HBV-DNA positive on 01-JAN-10 and whose ALT reached $\geq 5 \times$ ULN on 01-APR-10, the date of viral reactivation is 01-APR-10).

Screening for Hepatitis C

Patients with a positive Hepatitis C test or known to have a history of HCV infection including those with a negative viral load test at baseline are excluded from the study.

All interruptions or changes to study drug administration must be recorded.

It will be documented whether or not each patient completed the clinical study. If for any patient either study treatment or observations were discontinued the reason will be recorded.

Reasons that a patient may discontinue participation in a clinical study are considered to constitute one of the following:

- adverse event(s)
- abnormal laboratory value(s)
- abnormal test procedure result(s)
- disease progression
- protocol violation
- subject withdrew consent
- lost to follow-up
- administrative problems
- death

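### Table 3-3 restarts RAD001 after hepatitis B reactivation with no grade limit, so a life-threatening (grade 4) case that Table 3-1 would discontinue can be rechallenged on HBV-DNA alone

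*Combined protocol and SAP*

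**What the plan says.** Section 3.2.6.4, Table 3-3, has one row for patients with positive HBV-DNA or HBsAg at baseline and one for patients negative on both but antibody-positive. Each row starts an antiviral and holds the drug: "Interrupt study drug administration until resolution: ≤ baseline HBV-DNA levels". The first row continues: "If resolution occurs within ≤ 28 days, study drug should be re-started at one dose lower, if available". The second says the same: "If resolution occurs within ≤ 28 days study drug should be re-started at one dose lower, if available". For a patient already at the lowest level, "the patient should restart at the same dose after resolution". If resolution takes more than 28 days, RAD001 is discontinued.

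The table's header covers reactivation whether or not the patient has symptoms. Its footnote records every reactivation as grade 3, "unless considered life threatening by the investigator; in which case they should be recorded as grade 4". No action is attached to that grade 4.

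Section 3.2.3 sends unacceptable toxicity to Table 3-1. There, grade 4 non-hematological toxicity means discontinuation, with hyperlipidemia as the only exception. Table 3-1 hands grade 2 and 3 pneumonitis to Table 3-2a and grade 3 or higher hyperlipidemia to Section 3.2.6.2. It hands nothing to Table 3-3.

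Other text sends reactivation to Table 3-3. Section 3.2.5j says "For guidance on management of Hepatitis B and C reactivation, refer to Section 3.2.6.4", and Section 3.2.6.4 says "For hepatitis B reactivation, definition and management guidelines, see Table 3-3 Guidelines for management of hepatitis B". Footnote 3 of the visit schedule (Section 3.4.1) makes it mandatory to interrupt or discontinue according to Table 3-3 once reactivation is confirmed. Section 3.2.5 describes Table 3-1 as general recommendations.

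**The concern.** A grade 4 reactivation whose HBV-DNA clears within 28 days meets two opposite instructions: restart under Table 3-3, discontinue under Table 3-1. The pointers in the text favour Table 3-3. On that reading the protocol directs rechallenge with the suspected drug after a life-threatening event, on a virological criterion alone. Table 3-3 requires neither liver-enzyme nor clinical recovery before the restart. Table 3-1 is stricter even one grade lower: after grade 3 non-hematological toxicity, RAD001 waits for recovery to grade 1 or better.

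What is at stake is the safety of an individual patient, and consistent handling of such a patient across a multi-center trial. The efficacy analysis is not involved.

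**Working it through.** The plan gives no figure to reproduce, so the check sets the rules side by side.

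**1. Does Table 3-3 reach grade 4?** Yes. Its header sets no severity limit and its footnote names grade 4. The restart rule in each row depends only on HBV-DNA and time.

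**2. Does Table 3-1 reach grade 4 reactivation?** On its wording, yes. The footnote to Table 3-3 codes reactivation under a CTCAE metabolic/laboratory term, which is non-hematological, and the grade 4 row excepts only hyperlipidemia. This assumes the event is suspected to be related to RAD001, which is the scope of Table 3-1.

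**3. What would the restart dose be?** From the dose levels in Table 3.0:
- 10 mg daily restarts at 5 mg daily.
- 5 mg daily restarts at 5 mg every other day.
- 5 mg every other day restarts unchanged.

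**4. When do the rules conflict?** Inputs: the 28-day window in Table 3-3; the Table 3-1 row for interruptions of 3 weeks or more (3 × 7 = 21 days); and the Section 3.2.4 rule for a delay of more than 21 days. Table 3-3 does not say when its 28 days start. I count all three from the interruption.

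| Days until HBV-DNA is at or below baseline | Table 3-3 | Table 3-1, grade 4 row | Table 3-1, 3-week row | Section 3.2.4 |
|---|---|---|---|---|
| Under 21 | Restart | Discontinue | Silent | Silent |
| Exactly 21 | Restart | Discontinue | Discontinue | Silent |
| 22 to 28 | Restart | Discontinue | Discontinue | Discontinue |
| Over 28 | Discontinue | Discontinue | Discontinue | Discontinue |

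Below 21 days the grade 4 row of Table 3-1 is the only written rule that stops the drug. If Table 3-3 displaces that row, no explicit stop rule for the reactivation remains.

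**5. Does a toxicity-specific table normally lift the grade 4 stop?** The closest comparison says no. Pneumonitis has its own Table 3-2a, and grade 4 there still means discontinuation. Grade 4 neutropenia may resume at a lower dose, but Table 3-1 says so expressly. Hyperlipidemia is exempt, again expressly. Nothing comparable is written for hepatitis B.

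**The case against.** The strongest reply is that the protocol already assigns this event. Footnote 3 of the visit schedule is mandatory wording that names reactivation and Table 3-3. Sections 3.2.5j and 3.2.6.4 point the same way, and Table 3-1 is called general. The missing hand-off in Table 3-1 may only be a cross-reference not updated when the hepatitis B text was added: Section 3.2.6.4 itself mentions patients treated before the amendment was approved.

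Much of this stands. A reader might infer that nothing in the protocol indicates which table prevails. The documents do not support that, because the pointers lean towards Table 3-3. But footnote 3 speaks of interrupting or discontinuing. It mentions neither restart, nor grade 4, nor Table 3-1. And if Table 3-3 does govern, the restart after a life-threatening event rests on HBV-DNA alone, so the reply does not remove the need for a change.

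A second reply is that sites would not act alone, and this also largely stands:
- Treatment ends at unacceptable toxicity (Section 3.3.1).
- Toxicity that interrupts treatment is followed at least weekly (Section 3.2.4).
- All grade 4 events go to the lead institution's IRB under the DF/HCC reporting rules (Section 3.4.5).
- Life-threatening toxicity is reported immediately to the Protocol Chair and IRB (Appendix D, Section 7.0).
- Participating investigators report each SAE to the overall principal investigator within 24 business hours, and follow up within 24 to 48 hours on whether the patient continues (Appendix D, Section 7.2).
- A liver event graded in its own right would fall under Table 3-1.

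A reader might infer that two sites would silently handle the same event in opposite ways. Central reporting makes that unlikely. What it does not do is give the central decision-maker a written rule for the restart.

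**Conclusion.** The point holds as a narrow safety correction of minor severity. The two tables give opposite actions for a grade 4 reactivation that resolves within 28 days. The likelier reading follows Table 3-3 and directs rechallenge, and no text exempts grade 4 reactivation from Table 3-1 or deals with restart after it.

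A reader might go further and infer that rechallenge is compulsory. The documents do not support that: Table 3-3 is titled as guidelines, says the drug should be restarted, and leaves the investigator free to stop for unacceptable toxicity.

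The case is rare, and the documents give no rate. Reactivation is described as sporadic (Section 3.2.5j), at most 50 patients are planned, cirrhosis and chronic active or persistent hepatitis are excluded, and Table 3-2 recommends antiviral prophylaxis for patients positive for HBV-DNA or HBsAg. The gap matters mainly when HBV-DNA clears in under 21 days. There is no effect on alpha or power. The conclusion assumes that reactivation is judged a suspected RAD001 toxicity and that the time limits run from the interruption.

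**What to change.** Add one line to each of the two serology rows of Table 3-3:

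> Grade 4 (life-threatening) reactivation: discontinue RAD001 permanently per Table 3-1; continue antiviral therapy at least 4 weeks after last dose.

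This matches the protocol's own grade 4 rule in Table 3-1 and its grade 4 pneumonitis rule in Table 3-2a. An unrestricted pointer from Table 3-1 to Table 3-3 would be the wrong repair. It would confirm the restart after grade 4, and it would take grade 3 reactivations out of Table 3-1's recovery condition and 3-week row, leaving only the 21-day rule in Section 3.2.4. If a pointer is added, it should say that the grade 4 rule of Table 3-1 prevails.

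The cost is two lines of text with no new assessments or data. It does need a protocol amendment, and because Appendix D, Section 5.4 lists a change of treatment among its examples of major amendments, full IRB approval may be required. The clinical downside is that a rare patient who recovers from a grade 4 reactivation loses study drug. The mismatch between the 28-day window and the 3-week rules also affects grade 3 reactivation. This change does not settle it, and it could be resolved in the same amendment.

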3.3 Treatments

3.3.1 RAD001 Administration

The study drug RAD001 will be self-administered (by the patients themselves). The investigator will instruct the patient to take the study drug exactly as specified in the protocol. RAD001 will be administered orally as once daily dose of *10 mg (one 10mg tablet or two 5mg tablets)* continuously from study day 1 until progression of disease or unacceptable toxicity. Patients will be instructed to take RAD001 in the morning, at the same time each day.

RAD001 should be taken by the patient in a fasting state or with no more than a light fat-free meal. Dietary habits around the time of RAD001 intake should be as consistent as possible

Version 12

Updated: 1/28/2014

throughout the study. Tablets should be swallowed whole with a glass of water. The tablets must not be chewed or crushed and grapefruit or citrus juices should be avoided. For patients unable to swallow tablets, everolimus tablet (s) should be dispersed completely in a glass of water (containing approximately 30mL) by gently stirring, immediately prior to drinking. The glass should be rinsed with the same volume of water and the rinse should be completely swallowed to ensure that the entire dose is administered.

A dose of RAD001 is considered missed if the patient did not take RAD001 within 6 hours of the scheduled time. If vomiting occurs, no attempt should be made to replace the vomited dose. All dosages prescribed and dispensed to the patient and all dose changes during the study must be recorded.

Medication labels will comply with US legal requirements and be printed in English. They will supply no information about the patient. The storage conditions for study drug will be described on the medication label. RAD001 will be provided by Novartis. RAD001 is formulated as tablets for oral administration of 5mg and 10 mg strength. Tablets are blister-packed under aluminum foil, which should be opened only at the time of administration as drug is both hygroscopic and light-sensitive. Patients will be given a two-months supply.

3.3.2 Treatment assignment

This is a non-randomized trial. In the first step of the trial, 18 patients with differentiated thyroid cancer will be enrolled and if responses are seen, the study will proceed to the full enrollment of 50 patients.

3.3.3 Concomitant therapy

Patients will be instructed not to take any additional medications (including over-the-counter products) during the course of the study without prior consultation with the investigator. At each visit, the investigator will ask the patient about any new medications he/she is or has taken after the start of the study drug.

All Concomitant medications/Significant non-drug therapies taken ≤ 30 days prior to start and after start of study drug, including physical therapy and blood transfusions, should be recorded.

The following restrictions apply during the entire duration of the study:

- No other investigational therapy should be given to patients.
- No anticancer agents other than the study medication should be given to patients. If such agents are required for a patient then the patient must first be withdrawn from the study.
- Growth factors (e.g. G-CSF, GM-CSF, erythropoietin, platelets growth factors etc.) are not to be administered prophylactically but may be prescribed by the investigator for rescue from severe hematologic events, if this is thought to be appropriate.

Concurrent administration of RAD001 and strong CYP3A4 inhibitors (such as ketoconazole, itraconazole, ritonavir) and inducers (such as rifampin, rifabutin) should be avoided.

Provided there is no alternative treatment available, patients should be closely monitored for potential toxicities.

Concurrent administration of RAD001 and moderate CYP3A4 inhibitors (such as erythromycin, fluconazole, calcium channel blockers, benzodiazepines) and moderate CYP3A4 inducers (e.g. carbamazepine, phenobarbital, phenytoin) should also be avoided if possible, or used subject to caution (e.g. increased frequency of safety monitoring, temporary interruption of RAD001).

Competitive inhibition could occur when RAD001 is combined with drugs which are also CYP3A4 substrates. Therefore caution should be exercised in such cases.

Co-administration with substrates, inducers, or inhibitors of P-glycoprotein should be avoided, if possible, or used subject to caution (e.g. increased frequency of safety monitoring, temporary interruption of RAD001).

Grapefruit, grapefruit juice and pomegranate juice affect cytochrome P450 and P-glycoprotein activity and should therefore be avoided.

- In addition, patients should avoid Seville oranges and star fruit, as well as the juice of these fruits, which are potent CYP3A4-inhibitors.
- No chronic treatment with systemic steroids or other immunosuppressive agents while taking RAD001. Topical or inhaled corticosteroids are allowed.
- In case of severe mucositis, systemic treatment with oral steroids for up to one week is allowed. RAD001 is held while on oral steroids.
- RAD001 may affect the response to vaccinations making the response to the vaccination less effective. Live vaccines should be avoided while a patient is treated with RAD001.

Oral anticoagulants such as warfarin are CYP2C9 substrates and, as such, no interaction with RAD001 is expected. However, drug-drug interaction studies between macrolide antibiotics and warfarin have produced mixed outcomes and the disparity in these findings has led to the conclusion that multiple factors may alter the clearance of warfarin. The coadministration of RAD001 and oral anticoagulants is possible but should be subject to verification of coagulation (INR) once steady state is reached (after one week's treatment).

Examples are provided in Table 3-3a. A comprehensive list of cytochrome P450 isoenzymes and CYP3A4 inhibitors, inducers, and substrates can be found at <http://medicine.iupui.edu/flockhart>. This website is continually revised and should be checked frequently for updates.

Table 3-3a Examples of clinically relevant drug interaction: substrates, inducers and inhibitors of isoenzyme CYP3A.

Substrates (competitive inhibition)	
Antibiotics ¹ : clarithromycin* erythromycin telithromycin* Anti-arrhythmics: quinidine Benzodiazepines: alprazolam diazepam midazolam triazolam Immune Modulators: cyclosporine tacrolimus (FK506) HIV Protease Inhibitors: indinavir* ritonavir* saquinavir* Prokinetic: cisapride Antihistamines: astemizole chlorpheniramine ³²	Calcium Channel Blockers: amlodipine diltiazem felodipine nifedipine nisoldipine nitrendipine verapamil HMG CoA Reductase Inhibitors ² : atorvastatin cerivastatin lovastatin simvastatin Miscellaneous: aprepitant buspirone haloperidol methadone pimozone quinine sildenafil tamoxifen trazodone vincristine
Inducers	
Carbamazepine Phenobarbital Phenytoin* Rifabutin*	Rifampin* St John's wort Troglitazone
Inhibitors	
Amiodarone Cimetidine Clarithromycin Delaviridine Diltiazem Erythromycin Fluvoxamine* Grapefruit juice Sevilla orange	Indinavir Itraconazole* Ketoconazole* Voriconazole* Posaconazole* Mibefradil Nefazodone* Nelfinavir* Troleandomycin Verapamil

Based on: Ingelman-Sundberg M, Human drug metabolising cytochrome P450 enzymes: properties and polymorphisms, Naunyn Schmiedebergs Arch Pharmacol. 2004 Jan;369(1):89-104. and [http://www.medicine.iupui.edu/flockhart/clinlist.htm as of July 13, 2006]

* asterisk denotes strong inhibition/ induction

Please note:

strong inhibitor implies that it can cause ≥ 5 -fold increase in AUC or $\geq 80\%$ decrease in clearance of sensitive CYP substrates

moderate inhibitor implies that it can cause 2 to 5-fold increase in AUC values or 50-80% decrease in clearance of sensitive CYP substrates.

(Distinction is not always categorical as interaction can vary according to conditions).

Macrolide antibiotics: Azithromycin is not a CYP3A substrate. It may therefore be employed where antibiotherapy with a macrolide is desirable in a patient being treated with RAD001

Statins: Atorvastatin and pravastatin may be associated with RAD001, since a PK interaction study has shown that there is no relevant PK interaction.

3.3.4 Treatment compliance

Records of study medication used, dosages administered, and intervals between visits will be recorded during the study. Drug accountability will be noted and patients will be asked to return all unused study medication.

3.4 Visit schedule and assessments

3.4.1 Visit schedule

The visit schedule is outlined in Table 3.4a below.

General/safety assessments	Study entry (within 14 days of day 1 unless otherwise noted))	Day1 ²	At office visit every 4 weeks ¹	Every 8 weeks for max. 24 months ¹
Informed consent	X (within 28 days of day1)			
Medical history, height and vital signs	X		X	
Inclusion/exclusion criteria	X			
ECOG Performance status	X	X	X	
QOL questionnaire (EQ-5D)		X	X	
MTC-related symptoms questionnaire (MTC subjects only)		X	X	
Physical examination and weight	X	X	X	
ECG	X			
AE's and con-medications/treatments	X	X	X	
Laboratory assessments				
Pregnancy test for WOCBP (female subjects <50)	X			
Coagulation tests	X			
Hepatitis B tests (Hep B Core, Hep B Surf AB, Hep B Surf AG, HBV DNA) ³	X (within 30 days of Day 1)		X (only HBV DNA if positive at baseline)	
Hepatitis C test (HCV RNA PCR) ³	X (within 30 days of Day 1)			
Hematology and blood chemistry	X		X	
Urinalysis	X			
Calcitonin and CEA if elevated at baseline (only MTC subjects)	X		X (if elevated at baseline)	
Thyroglobulin and anti-thyroglobulin antibodies (only DTC subjects)	X		X (if elevated at baseline) ⁴	
Free T4 and TSH	X		X	
Radiological assessments				
CT/MRI neck, chest, abdomen ⁵	X (within 30 days of day 1)			X
Whole body bone scan (only MTC, FTC, HCTC subjects)	X (within 30 days of day 1)			
First dose of Rad001		X ²		
Rad001 dispensed/returned				X

- ¹+/- one week depending on appointment availability due to holidays or unforeseen events
- ²First dose of RAD001 may start the morning of Study Day 2.

- ³All patients should be screened for hepatitis risk factors and any past illnesses of hepatitis B and hepatitis C infection. It is highly recommended that patients positive HBV-DNA or HBsAg are treated prophylactically with an antiviral (i.e. Lamivudine) for 1-2 weeks prior to receiving study drug (see Section 3.2.6.4). The antiviral treatment should continue throughout the entire study period and for at least 4 weeks after the last dose of everolimus. Patients on antiviral prophylaxis treatment or positive HBV antibodies should be tested for HBV-DNA on Cycle 1 Day 1 and Day 1 of all subsequent cycles (every 28 days) to monitor for re-activation. If re-activation is confirmed, everolimus must be interrupted or discontinued according to the guidance in Table 3-3. Patients with viral hepatitis C risk factors should be screened for HCV RNA-PCR. Patients with positive HCV RNA-PCR results at screening and/or a history of past infection (even if test at baseline is negative) will be ineligible for the study.
- ⁴**Thyroglobulin and thyroA are both drawn at monthly visits only if AT BASELINE thyroA lab value is negative AND thyroglobulin value is elevated.**
- ⁵CT/MRI scans are to be performed every 2 months until first progression or death through 24 months from study entry. Post 24 months, if a patient has already stopped study treatment, but still alive without first progression, follow for first progression (CT/MRI scans every 3 months) and survival through 5 years from study entry. Post 24 months, If patient is scheduled to continue treatment, follow for first progression (CT/MRI scans every 3 months) and survival through 5 years from study entry; If treatment is stopped post 24 months but prior to 5 years from study entry for reasons other than progression, follow for first progression and survival through 5 years from study entry; if treatment is stopped post 24 months but prior to 5 years from study entry due to first progression, follow until death or 5 years from study entry, whichever is first.;

